15.2.2 Pharmacokinetic Parameters

PK parameters for AZP-3601 will be estimated using non-compartmental methods with WNL under PK population set with data handling of PK Data Set and PK Data Set Info (if meaningful by the data obtained). Parameters will first be derived with values under LLOQ set as "BQL" (i.e. using PK Data Set). The inclusion of the informative PK concentrations ("No peak" and actual value between 0 and the LLOQ) in the calculation of the parameters will be performed for information only (i.e. using PK Data Set Info). Descriptive statistics will be conducted on both data sets if meaningful by the data obtained.

The plasma PK parameters will be estimated from the concentration-time profiles. In estimating the PK parameters, BQL values at the beginning of the profile will be set to zero. BQL values that occur after the first quantifiable point will be considered missing. Values that are embedded between BQLs, or quantifiable values occurring after two or more BQLs, will be set to missing at the discretion of the pharmacokineticist. Actual sampling times, rather than scheduled sampling times, will be used in all computations involving sampling times. If the actual time or dose time is missing, the scheduled time may be substituted in order to calculate the PK parameter.

EDSREP 009 T 01 G Page 24 of 53

Version Date: 26-Aug-2022

The points to be included in the k_{el} range will be determined by the pharmacokineticist after inspection of the semi-log concentration-time profiles. At least 3 points will be required to be used. The C_{max} data point will not be included.

Parameters based on %AUC $_{extra}$ >20% or Adj R 2 \leq 0.80 will be flagged but not excluded from statistical analysis.

Descriptive statistics (n, arithmetic mean, SD, geometric mean, geometric CV(%), median, min, and max) will be used to summarize the calculated PK parameters by study part and treatment (for Parts A and B) /cohort (for Part C). For t_{max}, only n, median, min and max will be presented.

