If independence from active vitamin D and reduction of oral calcium is not achieved on Day 14 (ie, elimination of active vitamine D and reduction of oral calcium to or below 500 mg/day), the AZP-3601 dose will be increased and patients will be treated at this dose for the remaining duration of the treatment period (up to Day 28). In addition, staggered reductions of doses of oral calcium and active vitamin D supplements will therefore be performed and/or continued during the second 14 days of the Main Treatment Period according to the same principles as the first 14 days of the Main Treatment Period.

Patients achieving independence from active vitamin D and reduction of oral calcium on Day 14 will remain at the same dose level. The last remaining daily dose of oral calcium, if any, may be removed on Day 17 based on the predose albumin-corrected value of serum calcium.

Patients will undergo frequent testing for albumin-corrected serum calcium and phosphate during the initial 14-day treatment period and again following increase of the dose. In addition, there may be additional and unscheduled checks for albumin-corrected serum calcium and phosphate at the discretion of the Investigator.

At any time during the study, hypercalcemia and hypocalcemia will be managed by adjustment in active vitamin D and/or oral calcium supplementation. Adjustments will be based on laboratory values including albumin-corrected serum calcium and serum phosphate as well as on symptoms and will be performed at the Investigator's judgment. As a general guidance, adjustments should be performed when calcium values are outside the target range of 7.8 to 9.0 mg/dL, ie, 1.95 to 2.25 mmol/L.

The following treatments are administered in Part C in an open-label fashion:

- Cohort C1: multiple sc doses of 20 µg AZP-3601 (n=12) qd from Day 1 to Day 28 (dose increase of AZP-3601 to 40 µg was allowed from Day 14 onwards)
- Cohort C2^b: multiple sc doses of a fixed dose of 10^a µg AZP-3601 (n=12) qd from Day 1 to Day 28 (dose of AZP-3601 may be increased at a fixed dose of 20^a µg from Day 14 onwards)

During the extension phase, patients may have their AZP-3601 dose increased in increments of 10^a µg to a maximum dose of 60^a µg (Cohort 1) and of 80^a µg (Cohort 2)

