5.0 Study Objectives

5.1 Primary

•

- To assess the safety and tolerability of AZP-3601 following single and 4-week multiple ascending doses administered by sc injection to patients with hypoparathyroidism (HP) (Part C, Main Treatment Period)
- To assess the safety and tolerability of AZP-3601 during a 2-month treatment extension period (Part C, Extension Phase) in patients with HP

EDSREP 009 T 01 G Page 4 of 53

Protocol: AZP-3601-CLI-001 Version Date: 26-Aug-2022

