14.0 Treatment Compliance and Exposure

Exposure data of study drug, collected by CRF, will be listed by subject. In Part C, exposure data of study drug, collected by diary, will also be listed by subject. If applicable, date and time of meal intake and comments will be listed.

For Part C, exposure data of study drug will be summarized by cohort for

- Dose exposure parameters separately by main treatment period and extension phase include:
 - o Total actual dose received (µg) (Sum of all doses administered)
 - Number of doses received
 - Duration of exposure (in days) = last dose date first dose date + 1
 - Dose Intensity (μg/day) = total actual dose received / duration of exposure
 - o Relative Dose Intensity (ratio) = total actual dose received / total planned dose
- Dose increases during the main treatment period include:
 - o Doses increases at Day 15 = Yes / No (doses at Day 15 versus doses at Day 1)

EDSREP 009 T 01 G Page 19 of 53

Version Date: 26-Aug-2022

- Doses increases after Day 15 = Yes / No (doses at Day 16 or later up to Day 28 versus doses at Day 1)
- Doses increases or decreases during the extension phase (versus actual dose at Day 28) include:
 - Number of patients with one increase only (without decrease)
 - o Number of patients with at least two increases (without decrease)
 - Number of patients with one decrease only (without increase)
 - Number of patients with at least two decreases (without increase)
 - o Number of patients with both increase and decrease
 - o Number of patients with no change in dose

Study drug dispensing and returning will be listed by subject.

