15.2 Pharmacokinetic Summaries

15.2.1 Pharmacokinetic Concentrations

All AZP-3601 plasma concentrations will be reported under PK population set with data handling of PK Data Set and PK Data Set Info (for information only). Under PK Data Set, analyses on the concentrations will be performed with values under LLOQ set as "BQL". Under PK Data Set Info, AZP-3601 plasma concentration will include the concentrations extrapolated from the analyte response under the LLOQ (for information purpose); values under LLOQ will either be a "No peak" or an actual value between 0 and the LLOQ value (i.e. 50 pg/mL). The Inclusion of the informative PK concentrations ("No peak" and actual value between 0 and the LLOQ) in the analyses under PK Data Set Info will be performed for information only. The conventions to be applied for "No peak" under PK Data Set Info will be the same as the one use for BQL under PK Data Set. Descriptive statistics and PK concentration plots will be conducted on both data sets.

Descriptive statistics (n, 0<n<LLOQ, n with imputed 0, arithmetic mean, SD, geometric mean, geometric CV(%), median, min, and max) will be used to summarize the plasma concentrations for AZP-3601 by scheduled time point by study part and treatment (for Parts A and B)/cohort (for Part C). Plasma concentrations for AZP-3601 below the quantifiable limit (BQL) will be set to zero in the computation of descriptive statistics. Geometric means and geometric CV(%) will be presented as 'NC' (not calculable) if there is at least one BQL value imputed by zero.

Linear and semi-logarithmic plots of the arithmetic mean plasma concentration with SD by scheduled
sampling time will be provided by study part and
plots will show time in hours. In Part
C, the MAD treatments will be presented in one plot per day. In addition, overlay plots for the MAD
treatments will be presented,
showing Day 1, Day 14 and Day 28 in one plot for Part C (one plot per cohort). If more than half of the subjects for a given timepoint have BQL values, then no mean profiles will be provided.
Combined individual concentration-time profiles will be presented graphically on both a linear and a semi-logarithmic scale for each

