17.1.1 Adverse Events

A treatment-emergent adverse event (TEAE) is defined as any event not present prior to (the first) administration of the study drug or any event already present that worsens in either severity or frequency following exposure to the study drug.

An overall summary table will be provided by treatment and overall for each study part with the number of subjects and events reporting, AEs, TEAEs, treatment-emergent SAEs, treatment-emergent AEs of special interest (AESIs), and TEAEs leading study drug discontinuation.

Based on the pharmacology of AZP-3601 as well as other PTH analogs, and the pathophysiology of HP, AESIs are as follows:

- Hypocalcemia (including the following symptoms: agitation, anxiety, hypoestesia, paresthesia, muscle cramping, muscle fatigue, musculoskeletal pain, musculoskeletal stiffness, myalgia, tetany, seizure, tremor, brain fog).
- Hypercalcemia (including the following symptoms: thirst, frequent urination, abdominal pain, nausea, vomiting, fatigue).
- Hypercalciuria.
- Orthostatic hypotension and vasodilatory symptoms (including postural/orthostatic dizziness, syncope, tachycardia/palpitations).

A summary table with the number of subjects reporting TEAEs and the number of events, categorized by system organ class (SOC) and preferred term (PT) coded according to the MedDRA, will be presented by /cohort (for Part C) and overall for each study part. Subjects will only be counted once within each system organ class or preferred term.

A summary table with the number of subjects reporting TEAEs, categorized by SOC, PT and relationship to study drug (Related or Not Related), will be provided by //cohort (for Part C) and overall for each study part. A treatment-related TEAE is defined as any TEAE that is assessed by the investigator as definitely, likely, possibly or unlikely related to study treatment. TEAE that is assessed as Not Related will be defined as not treatment-related. Subjects with multiple events within a particular body system or preferred term will be counted under the category of their most drug-related event within that body system or preferred term.

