A summary table with the number of subjects reporting TEAEs, categorized by SOC, PT and severity as recorded on eCRF (Mild, Moderate, Severe, Life-threatening or Death), will also be provided by cohort (for Part C) and overall for each study part. Subjects with multiple events within a particular body system or preferred term will be counted under the category of their most severe event within that body system or preferred term.

A summary table with the number of subjects reporting treatment-emergent AESIs and the number of events, categorized by SOC and PT coded according to the MedDRA, will be presented by treatment (for Parts A and B)/cohort (for Part C) and overall per for each study part. Subjects will only be counted once within each body system or preferred term.

The following missing data will be imputed as defined (for calculations only / will not be presented):

- Missing AE severity or relationship will be assumed to be severe or related, respectively
- Missing AE start times for the determination of treatment emergence will be assumed to occur after treatment unless partial date documents the AE as happening prior to treatment
- Missing AE start date will be assumed to be after treatment for the determination of TEAE unless partial or complete end date documents the AE as happening prior to treatment

All AEs (including non-treatment-emergent events) recorded on the eCRF will be listed, with a flag to indicate whether the AEs are AESIs.

A separate listing of TEAEs leading to study drug discontinuation will be provided.

EDSREP 009 T 01 G Page 31 of 53

Protocol: AZP-3601-CLI-001 Version Date: 26-Aug-2022

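### Part C PK summaries by cohort pool different doses at Days 28 and 84, and the accumulation ratio has no stated dose correction

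*SAP*

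**What the plan says.** **PK grouping.** SAP 15.2.1 summarises plasma concentrations "by scheduled time point by study part and treatment (for Parts A and B)/cohort (for Part C". SAP 15.2.2 uses the same grouping for parameters: statistics "will be used to summarize the calculated PK parameters by study part and treatment (for Parts A and B) /cohort (for Part C". SAP 15.2.1 also plans an overlay plot of Days 1, 14 and 28, one per cohort.

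**Dose within a cohort.** In the protocol synopsis (Part C treatments), C1 starts at 20 µg and may go to 40 µg; C2 starts at 10 µg and may go to 20 µg. The dose is raised in patients who have not met the supplement-reduction goal on Day 14. "During the extension phase, patients may have their AZP-3601 dose increased in increments of" 10 µg, to at most 60 µg (C1) or 80 µg (C2). Reductions are allowed at any time.

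**Labels.** SAP 8.2.2 defines the Part C dose level as the cohort, with the increase inside it, and gives C2 as 40 µg with an increase to 60 µg. SAP 6.0 likewise has up to 40 and up to 60 µg.

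**Parameters.** In SAP Table 1, Rac for Part C is the 6-hour AUC on Day 28 over that on Day 1, with no dose term. CLss/F is dose divided by AUC.

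**Dose changes.** SAP 14.0 tabulates "Doses increases at Day 15 = Yes / No (doses at Day 15 versus doses at Day 1" and counts increases and decreases in the extension. Nothing visible links these to PK records or adverse events.

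**Adverse events.** In SAP 17.1.1 the severity table "will also be provided by cohort (for Part C) and overall for each study part" and the AESI table "will be presented by treatment (for Parts A and B)/cohort (for Part C) and overall per for each study part". The top-level table is worded differently: "An overall summary table will be provided by treatment and overall for each study part".

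**The concern.** In a conventional ascending-dose study, a column headed by cohort is a column headed by dose. In Part C that is true only until the first dose change. From then on, a cohort mean of Cmax or AUC averages over whatever mix of doses its patients have reached, and its CV adds the spread of doses to the spread between patients. One dose is also divided between columns: under the protocol, 20 µg is both the C1 starting dose and the C2 increased dose.

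Rac raises a separate problem. It compares each patient's Day 28 with the same patient's Day 1. If the dose has doubled in between, the ratio roughly doubles even when nothing accumulates. That is bias in a named parameter, not only extra noise, and the overlay plot would show the same artefact.

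The SAP's primary objective is "To assess the safety and tolerability of AZP-3601 following single and 4-week multiple ascending doses". Secondary objectives are PK over ascending doses and whether individual titration over a dose range is feasible. Readers will look to these tables for exposure at each dose and for evidence of accumulation.

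**Working it through.** The plan gives no sample size, power or CV figure to reproduce. The check is of dose ratios and of what pooling does to the reported statistics.

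**1. Dose ratios**

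| | Protocol doses | SAP doses for C2 |
|---|---|---|
| C1 after Day 14 | 40/20 = 2.0 | – |
| C2 after Day 14 | 20/10 = 2.0 | 60/40 = 1.5 |
| C1 extension maximum over start | 60/20 = 3.0 | – |
| C2 extension maximum over start | 80/10 = 8.0 | 80/40 = 2.0 |

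**2. Which days are affected**

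- Day 1: every patient in a cohort is on the starting dose, so there is no pooling.
- Day 14: probably the starting dose. The protocol speaks of an initial and a second 14 days and, at Day 28, of the dose of the previous 14 days. SAP 14.0 looks for the increase at Day 15. Only the protocol wording that permits the increase from Day 14 on points the other way.
- Days 28 and 84: pooled whenever patients in the cohort are on different doses.

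**3. Bias in Rac.** Assume exposure proportional to dose and a share p of the cohort doubled. Each doubled patient's Rac is multiplied by 2, so the geometric mean is multiplied by 2^p.

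- p = 0.25 (3 of 12): 2^0.25 = 1.19
- p = 0.50 (6 of 12): 2^0.50 = 1.41
- p = 0.75 (9 of 12): 2^0.75 = 1.68

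These are what a true Rac of 1.0 would be reported as. The Day 28 geometric means of Cmax and AUC exceed their starting-dose values by the same factors.

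**4. Inflated CV at Day 28.** SAP 8.1.3 defines geometric CV as sqrt(exp(s²) − 1) × 100. Pooling adds the variance of ln(dose), which is p(1 − p)(ln 2)², to the within-dose log-variance ln(1 + CV²). For p = 0.5 the addition is 0.25 × 0.480 = 0.120.

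- True CV 20%: reported 42%
- True CV 30%: ln(1.09) + 0.120 = 0.086 + 0.120 = 0.206; sqrt(exp(0.206) − 1) = 48%
- True CV 50%: reported 64%

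With p = 0.25 or 0.75, a true 30% shows as 44%.

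**5. Inflated CV at Day 84.** Assume doses spread evenly in 10 µg steps and a true CV of 30%.

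| Range | Reported CV | Patients per level |
|---|---|---|
| C1, 20–60 µg | 52% | 12/5 = 2.4 |
| C2, 10–80 µg (protocol start) | 82% | 12/8 = 1.5 |
| C2, 40–80 µg (SAP start) | 40% | 12/5 = 2.4 |

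The true CVs, the share doubled and the spread of extension doses are assumptions; the documents give none of them.

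**The case against.** The strongest reply is that Part C assigns a titration regimen, not a fixed dose. Cohort is then a legitimate reporting unit, especially where feasibility of individual titration is itself an objective. The study is also exploratory, with no hypothesis tests, so no error rate or decision rule is affected. Both points stand. They support keeping the cohort tables, but they do not repair Rac or make a pooled Day 28 or Day 84 Cmax interpretable.

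A reader might go further and infer that no Part C exposure or safety result belongs to a dose level, and that the planned outputs cannot address the objectives at all. The documents do not support that:

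- Day 1 is one dose per cohort, and Day 14 probably is too.
- CLss/F and Vz/F are dose-normalised by formula.
- Main period and extension are reported separately.
- Exposure, individual PK profiles and all adverse events are listed by subject, so an event can be traced to a dose by hand.
- The overall adverse-event table is by treatment. SAP 8.5 equates treatment with dose levels, whereas SAP 8.2.2 gives Part C a single treatment, so this is ambiguous rather than absent.
- SAP 15.2.2.1 on dose-proportionality has a heading but no text in the public version, part of the grouping phrase for the mean plots is cut, and the table shells are not supplied. Nothing can be concluded from those gaps.

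A reader might also quote a 6- to 8-fold dose range in the extension. For C1 the range from the starting dose is 3-fold; 6-fold needs a reduction to 10 µg, which the text neither names nor excludes. The 8-fold range for C2 holds only with the protocol's starting dose.

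The objection is strongest on adverse events. Dose follows response, supplements change at the same time, and an even spread leaves about 1.5 to 2.4 patients per level. Hypocalcemia and hypercalcemia by dose at onset would be confounded.

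**Conclusion.** The concern holds for Day 28 and Day 84 concentrations, Cmax and AUC, and most clearly for Rac. Under dose-proportional exposure, a true Rac of 1.0 is reported as 1.19 to 1.68 with 25% to 75% of a cohort doubled. If exposure rises less than in proportion to dose, the bias is smaller. With SAP doses for C2 (1.5-fold), the factor at 50% increased is 1.5^0.5 = 1.22 instead of 1.41. The Day 84 CVs rest on an assumed even spread and are illustrations only.

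For adverse events the point is weaker. The detailed tables by cohort do not show the dose in use, but a table by dose would be descriptive and confounded, so it is a supplement and not a correction. The change is worth making because it removes a bias and an inflated CV at little cost; it does not call the design into question.

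**What to change.** 1. **SAP 15.2.1 and 15.2.2:** keep the cohort tables. Add Day 28 and Day 84 concentrations, Cmax and AUC by the actual dose on the sampling day. Where a dose has few patients, give Cmax and AUC dose-normalised by cohort instead, noting that this presumes dose proportionality. List each profile with its dose.
2. **SAP Table 1:** compute Rac from dose-normalised AUC, or only in patients whose dose did not change between Day 1 and Day 28. State which. The second option needs no proportionality assumption but uses a selected subset.
3. **SAP 17.1.1:** show dose at onset in the adverse-event listings. As a descriptive supplement, tabulate TEAEs and AESIs by dose at onset with patient-days at each dose. Add a footnote that dose follows response, supplements change concurrently and groups are small. State what treatment means for Part C in the overall table, since SAP 8.2.2 and 8.5 differ.
4. **Reconcile** the protocol's allowance of an increase from Day 14 with the SAP's Day 15 check, so that the dose behind each Day 14 profile is known.
5. **Reconcile** the C2 doses in the protocol (10/20 µg) with those in SAP 6.0 and 8.2.2 (40/60 µg). The dose labels depend on both items.

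The cost is SAP wording and a few additional outputs. Dosing is already collected by CRF and diary under SAP 14.0, so no new data are needed. The limitation is sparse, non-randomised dose groups, which the footnote should make plain.

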15.2.2.1 Dose-Proportionality

16.0 Pharmacodynamic and other Analysis

16.1 Pharmacodynamic and other Variables

16.1.1 Serum PD Concentrations and Parameters

Part C:

At the time points defined in the schedules of assessments, blood samples will be taken for the measurements of serum total calcium, serum albumin, albumin-corrected serum calcium, serum phosphate, serum creatinine (to calculate the fractional excretion (FECa) of calcium and phosphate), and endogenous serum PTH(1-84).

Serum PD variables include level/concentration of

- Serum total calcium
- Albumin-corrected serum calcium
 - Albumin-corrected serum calcium (mmol/L) = serum total calcium (mmol/L) + 0.020 (40 serum albumin [g/L])
- Serum phosphate
- Endogenous serum PTH(1-84).

Furthermore, serum AUC_{0-24} for albumin-corrected calcium is a serum PD variable, which is defined as area under the serum concentration-time curve from time zero up to 24 hours for albumin-corrected calcium.

EDSREP 009 T 01 G Page 25 of 53

Version Date: 26-Aug-2022

Part only:

In addition to the PD variables listed above, at the time points defined in the schedules of assessments, blood samples will be taken for the measurements of serum 25-hydroxy vitamin D, serum 1.25-dihydroxy vitamin D, serum magnesium and serum bone turnover biomarkers.

Serum PD variables include level/concentration of

- Serum 1.25-dihydroxy vitamin D
- Serum Magnesium
- Serum bone turnover biomarkers:
 - Serum bone-specific alkaline phosphatase (BSAP)
 - Serum carboxy-terminal telopeptide of type I collagen (s-CTx)
 - Serum procollagen type 1 amino-terminal propeptide (P1NP)
 - o Serum osteocalcin

Part C only:

In addition to the PD variables listed above, the following serum PD variables will be calculated:

- Serum calcium phosphate product
 - Serum calcium phospate product (mg2/dL2) = serum total calcium (mg/dL) * serum phosphate (mg/dL)
- Number of patients within the target range of albumin-corrected serum calcium
- Number of patients within the normal range of albumin-corrected serum calcium
- Number of patients within target range of albumin-corrected serum calcium who taking no vitamin D
 and taking <=500mg of oral calcium
- Number of patients within normal range of albumin-corrected serum calcium who taking no vitamin D and taking <=500mg of oral calcium,

where target range refers to 7.8 to 9.0 mg/dL and normal range refers to 8.3 to 10.6 mg/dL.

